1.5 Nitric Oxide Nasal Spray Effects in Humans

The Sponsor has conducted Phase 1 and Phase 2 clinical trials to help establish the safety of NORS as a localized topical antimicrobial and further demonstrate the lack of a systemic toxicity signal as measured by methemoglobin. These trials also provide environmental safety data demonstrating that nitrogen dioxide (NO₂) levels remain below detection limits and far below Occupational Safety & Health Administration (OSHA) guidelines.

1.5.1 Nitric Oxide Nasal Spray (NONS) for the Treatment of Mild COVID-19 Infection Trial

In 2020, the Sponsor conducted a double-blinded, placebo-controlled trial that involved 79 adults diagnosed with mild COVID-19 in the community (confirmed by polymerase chain reaction [PCR]). Participants were randomly assigned to treatment with NONS or placebo (saline solution) at day 1. Nasal and throat swabs were collected at presentation for baseline followed by collection at Days 2, 4 and 6 which were 1, 3 and 5 days after starting treatment, respectively. Quantitative real-time reverse-transcriptase polymerase chain reaction (qRT-PCR) was performed to determine SARS-CoV-2 RNA. Nitric oxide nasal spray, started on or before day 5 of symptom onset, was independently associated with a significantly accelerated decrease in SARS-CoV-2 RNA concentration of -1.21 log₁₀ copies/ml on both Days 2 and 4, as compared to placebo. Therefore, the mean SARS-CoV-2 RNA concentration was lower for NONS, as compared to placebo, by a factor of 16 at both Days 2 and 4. Day 6 equated to at least 10 days since symptom onset and significant reduction of SARS-CoV-2 with or

without treatment was expected. Nevertheless, the SARS-CoV-2 RNA concentration was still lower on NONS at Day 6. The primary endpoint was a reduction of viral load from Day 1 through Day 6 (measured as area under the curve). Analysis revealed a mean difference of 5.22 log₁₀ copies/ml between NONS and placebo. This difference was shown to be significant with a P value of 0.0096. The average viral log reduction in the first 24 hours, in treatment arm was -1.362 which correlates to about 95%, while the average viral log reduction in the control (saline) arm was -0.15 which correlates to about 30% In addition, the majority of patients in this study were positive for SARS-CoV-2 variants of concern (VOC202012/01) also commonly known as the UK variant (European Medicines Agency 2020).

1.5.2 Nitric Oxide Nasal Spray COVID-19 Prevention Trial

In 2020, the Sponsor closed enrollment of a Health Canada (HC) trial (NCT04337918) to evaluate the safety and efficacy of NORS to prevent infection from SARS-CoV-2. In total, 143 participants were enrolled, and 103 participants received the NORS interventions in the form of NONS. Over 7,000 doses of NONS were administered in this trial and there were no reports of serious adverse events (SAEs) or significant adverse reactions (ARs) related to NONS specifically. Some participants reported adverse events (AEs) of mild nasal irritation which quickly resolved. None of the participants in the intervention arm (N=103) tested positive for COVID-19 during the study. However, no participants in the control arm (N=40) tested positive either so efficacy was not shown.

1.5.3 Nitric Oxide Nasal Spray Background

The NORS formulation is manipulated to achieve a safe dose that is microbicidal within minutes to viral and bacterial pathogens. Specific to pathogens related to sinusitis, it is called Nitric Oxide Nasopharyngeal Irrigation (NONI) or Nitric Oxide Gargle (NOG) or Nitric Oxide Nasal Spray (NONS). Based on scientific data (see Investigator Brochure Version 1,0 for details) the NO releasing capability of these products, should act as a nitrosative viricidal agent, may have beneficial restorative mucociliary and anti-inflammatory effects in participants with Flu/COVID-19.

Prevention is essential in controlling the spread of COVID-19. The Sponsor's nitric oxide nasal spray (NONS) would provide a new daily preventative measure as an easy-to-use prophylaxis. Nitric oxide nasal spray aims to initially reduce the pathogen load in the nasal passages where viruses first enter and reside and then blocks viral entry before they can penetrate the cells lining the nose.

Nitric oxide nasal spray will be self-administered throughout the day. The intervention solution will be delivered in a manual pump nasal spray container with 25 mL of solution. Each spray will dispense approximately $130\text{-}150\mu\text{L}$ of solution. Topical delivery of NONS will be performed after the individual blows their nose, with 4 nasal sprays at a time (two in each nostril) 3 times per day.

2 STUDY OBJECTIVES AND ENDPOINTS

2.1 Primary Objective and Endpoint

Objective	Endpoint	
To assess the efficacy of NONS in the reduction of risk of COVID-19 infection	Confirmed positive COVID-19 test (Both antigen and SARS-CoV-2 RT-PCR are acceptable) by Day 28. Positive test results based on sample collection within 48 hours of randomization will be considered infected at randomization and not counted as events.	

Abbreviations: NONS=nitric oxide nasal spray; RT-PCR=real-time polymerase chain reaction.

2.2 Secondary Objectives and Endpoints

Objective	Endpoint	
To assess the efficacy of NONS in prevention of severe COVID-19	Hospitalization or ER/ED visits for COVID-19/flu-like symptoms by Day 28	
Assess tolerability of NONS in participants with all participants including those with COVID-19	AEs and discontinuation of treatment	

Abbreviations: AE=adverse events; ER/ED=emergency room, emergency department NONS=nitric oxide nasal spray.

3 INVESTIGATIONAL PLAN

3.1 Overall Study Design and Plan

This is a multicenter, randomized, double-blinded, placebo controlled, Phase 3 clinical efficacy study evaluating NONS in healthy adult volunteers as a prevention treatment for individuals at risk from COVID-19 infection.

Up to 13,000 adult participants aged 18 or over with no known history of SARS-CoV-2 infection will be randomized into one of two cohorts of this study in a ratio of 1:1 (Treatment: Placebo Control). Participants with or without underlying medical conditions will be eligible to enroll. The NONS formulation proposed for use in this COVID-19 clinical study will be self-administered at a maximum of 3 times per day, morning, noon, and night for 28 days. Participants will be on study for 4 weeks of treatment (to include 5 days of Screening, 1 week of Follow-Up, participants will be followed for a total of approximately 5 weeks) as a viricidal Investigational Medical Product.

Participants will self-administer a nasal spray containing either blinded study treatment or placebo (herein called study treatment). Nitric oxide nasal spray (NONS) will be delivered from manual pump nasal spray container with 25 mL of solution with each nasal spray dispensing approximately 130-150 μ L of solution. After the subject blows their nose, each treatment will require two sprays per nostril, or about 0.5 mL per treatment.

The primary endpoint is to assess the efficacy of NONS in the prevention of COVID-19 infection as determined by a positive COVID-19 test (antigen or reverse-transcriptase polymerase chain reaction [RT-PCR]),

The secondary endpoints are to determine the proportion for participants requiring hospitalization or emergency room (ER/emergency department [ED]) visits for COVID-19 or flu-like symptoms by Day 28 and assess the safety and tolerability of use of NONS in participants with COVID-19.

This study will be a multicenter trial, allowing remote and in-person on-site visits, including telephone contact, as applicable per respective country regulatory legislation. All data collection and monitoring to be primarily performed remotely (Clinical Trials Transformation Initiative 2018). Screening and enrollment will take place through an online portal and through telehealth assessments, unless in a region that does not accept an eICF, in which case the consenting procedure will occur in-person on-site (screening and baseline procedures may also be performed in-person on-site). Participants will receive study treatment shipped directly to their homes as described in Section 6.5., unless in a region (EU) where the participant must receive the study product directly from the sites' staff/physician. Participants in the EU will have three in-person visits (screening visit, baseline visit [unless screening and baseline can occur on the same day] and a post-treatment visit). Participants will enter their study treatment dates and times and describe any symptoms in an online questionnaire (Table 4), or paper diary if necessary. Study sites will maintain contact with all enrolled participants and regularly collect paper diaries to ensure timely data entry.

3.2 Rationale for Study Design and Control Group

3.2.1 Rationale for Use of Nitric Oxide for COVID-19 Therapy

SARS-CoV-2 is a novel, human-infecting coronavirus, termed COVID-19. COVID-19 is highly contagious, with a high virulence, and on March 11, 2020 it was declared by the World Health Organization a global pandemic. A study treating individuals with a viricidal agent like NORS could be advantageous for many reasons. This treatment could be used either for infection prevention or at the time of diagnosis when the virus is the most susceptible because it is still in the nose or in upper airways. This approach could prevent the population in viral outbreak areas from getting infected, mitigate the progression of the viral infection and spread of the disease from those who are infected already to others. Obtaining an early diagnosis when the patient has mild to moderate disease and treating them while spontaneously breathing, could translate in the reduction of morbidity and mortality. Thus, it could lower the burden on already limited healthcare resources.

3.2.2 Rationale for use of a Nitric Oxide Releasing Solution Spray (NONS) Formulation

It is hypothesized that a NORS formulation, delivered prophylactically or at early stages of COVID-19 exposure, will be well tolerated, and may have other beneficial secondary outcomes. In addition, due to nitric oxide's broad spectrum, non-specific antimicrobial (specifically viricidal) characteristics and its fundamental basic biochemical action, microbial drug resistance may even be avoided. This is especially important with the emergence of variants that reduce the effectiveness of vaccines.

Nitric oxide releasing solution will be delivered in a nasal spray formulation, referred to herein as nitric oxide nasal spray (NONS). Given the severity and persistence of the complications associated with COVID-19 infection, the Sponsor hypothesizes that nitric oxide delivered via NONS may prevent COVID-19 infection.

While there have been only minimal reported side-effects from the topical application of gaseous nitric oxide, there have been reported adverse side effects of nitric oxide releasing compounds. Specifically, the adverse effects associated with topical nitrate/nitrite application include skin rash, burning sensation, sensitivity and staining of the skin and are mostly associated with the carrier or the acid required for NO donor release (Weller, Price et al. 1997).

The dose for the NONS is based on preliminary in-vitro dosing studies, using H1N1 and H3N2 and SARS-CoV-2 viruses, and based on the highest tolerated dose in volunteers in previous clinical trials conducted by the Sponsor.

3.2.3 Rationale for Multicenter Trial Design

The study will be conducted in a blinded fashion in conjunction with a placebo control to remove evaluation biased by the expected effects of the study treatment.

If allowed by applicable legislation in the respective country, all data collection and monitoring will be remote through telehealth assessments and phone calls without performing on-person visits. This allows for broader geographic reach and rapid response, for easy access to areas that present with a higher prevalence of the COVID-19 infection.

In countries where only remote visits are applicable, all participant interactions with the Investigator will occur through telehealth assessments in the participant's home (see Section 6.6.2 and Section 6.6.3 for more details on telehealth assessments). The participant will receive study treatment directly to their home, unless in a region (EU) or other location where the participant must receive the study product directly from the sites' staff/physician. All study treatments will be self-administered. A completely remote option trial design allows for potentially faster and more diverse participant recruitment, improved participant retention, which may reduce missing data, and provides the participant with greater control, convenience, and comfort performing treatments in the home. The administration of treatments in the home may also be more representative of real-world administration and use of the study treatment post-approval.

3.3 Study Duration and Dates

Actual overall study duration or participant recruitment period may vary. The proposed study start is Q4 2021. A participant's time on the study is expected to last 5 weeks from enrollment. Subject participation will consist of 5 days of Screening/Baseline, and 28 days study treatment, followed by 7 days of Follow-Up for safety assessments. Participants should complete the study on Day 35.

For participants that test positive for COVID-19, Health Canada (HC)/FDA, or other applicable relevant local/national regulatory health authorities should be notified as applicable to the regional area. Participants that test positive for COVID-19 will be encouraged to complete early termination assessments and record their symptoms using the COVID-19 symptom list.

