5.3 Selection and Timing of Dose for Each Participant

After screening has been completed, participants will be randomized by an interactive web response system (IWRS) into one of two groups, one group of 6,500 for the NONS treatment and one group of 6,500 for placebo treatments. Following randomization, study treatment will be dispensed during the in-person on-site visit (as required by local/national regulations) or shipped directly to participants for immediate use and confirmation on the appropriate eCRF. Participants will be instructed to treat themselves 3 times daily, morning, noon, and night (or approximately every 8 hours) with the nasal spray for 28 consecutive days.

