6.6.1 Daily Treatment Diary and Questionnaire (eCRF)

The questionnaire and electronic treatment diary will record the compliance of treatments administered or missed. It will also ask if treatments were tolerated and report any side effects or other comments. There is also a discomfort/pain scale if needed. Refer to Section 8.7 for action to be taken in the event of the spray bottle malfunctioning. Paper diaries with comparable information and instructions will be available as backup for all participants or as primary collection instruments for participants without sufficient access to devices or internet connectivity.

All participants will be asked to fill out an online (or paper if required) daily treatment questionnaire and COVID-19 symptoms diary as described in the Schedule of Events (Table 4). The complete language and content of all of the questions is described in the Manual of Procedures.

Participants must have access to the internet and a device that reliability connects to the internet and is able to dial into telehealth assessment. In the event of an inability to access the electronic PRO, the process described in the MOP/IOP will be followed for completion of paper records.

If a participant develops clinical symptoms of COVID-19 (see Section 6.6.4), they/their emergency contact should make every effort to document these in a COVID-19 symptoms list (Appendix 2).

Participants who enroll in the study could be asymptomatic for COVID-19 at time of randomization; in which case, if the participant tests positive for COVID-19 within < 2 days (48hrs) of the baseline visit they will be considered unevaluable for the study endpoint and will be discontinued.

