6.6.2 In-Person On-Site/Telephone Contact

Study staff for sites requiring on-site visits will contact participants via telephone on Day 7 and 28 (all others performing remote monitoring will contact participants on Day 7, 28, and 35) as described in the Schedule of Events (Table 4) and confirm participants' current health status including presence of any COVID-19 symptoms (Appendix 2; Appendix 3), in addition to any ER or hospital visits that might have occurred as a result of COVID-19. Participants will also be asked about any challenges with administration or any AEs they may have experienced.

Participants who are hospitalized for any reason and are unable to attend their on-site visit / telehealth assessment or complete their daily diary should have their emergency contact notify study staff as soon as possible. Participants that are hospitalized for COVID-19 only are considered treatment failures. Participants that are hospitalized for any other reason may stay on the study at the discretion of the Investigator.

Follow-up visits (end of study and early termination assessments) will be performed preferably on-site (in countries where remote only conduct is not allowed), but if the participant is hospitalized, in quarantine or unable to visit the site in-person for any reasonable cause as per investigators' judgement, these visits may be performed remotely and will not be considered a protocol deviation. Follow-up of all adverse events must be completed as described in the protocol Section 7.

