6.6.5 Early Termination Assessment

Participants that discontinue the study early due to COVID-19 infection or are hospitalized for any reason are encouraged to attend the early termination assessment to the best of their ability. If the participant is unable to complete the treatment diary or attend the early termination assessment, the designated emergency contact is encouraged to submit this information on behalf of the participant to the best of their ability.

Protocol deviations to be recorded for this study include visit/phone/telehealth procedure deviations and noncompliance; PRO noncompliance; study medication dosing noncompliance; and dispensing deviations. A special emphasis will be placed on dosing errors, lack of completion of the required daily PRO reporting, and the incomplete return of study medication at the conclusion of the study.

Study medication noncompliance is defined as less than 80% of expected doses administered while on possible study treatment. PRO noncompliance is defined as less than 70% of possible reporting days of data recorded, eg. before a hospitalization, or an early termination.

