7.12.1 Removal of Participants from the Trial or Study Treatment

The Investigator may withdraw a participant from the study for any of the following reasons:

- A protocol violation occurs,
- A serious or intolerable adverse event occurs,
- A clinically significant change in a laboratory parameter occurs,
- The Sponsor or Investigator terminates the study, or
- The participant requests to be discontinued from the study.

A participant may choose to discontinue study treatment and/or withdraw from the study at any time. Participants who become pregnant during the study are to be withdrawn from study treatment. In the absence of a medical contraindication, every effort should be made by the Investigator to encourage participants who prematurely discontinue treatment to remain in the study as appropriate and, at a minimum, follow the participant for safety data collection.

7.12.1.1 **Discontinuation from Study Drug Treatment**

Participants may discontinue for the following reasons: any study drug related AEs that in the opinion of the Investigator, makes it unsafe for the participant to continue; any study drug related AE that repeats upon re-challenge.

A participant may be discontinued prematurely from study drug treatment for the following reasons:

- AE (including hospitalization for COVID-19/sequalae)
- Withdrawal by participant (specify reason in the eCRF)
- Lost to Follow-up
- Pregnancy

- Physician decision (ie, Investigator decision specify reason in the eCRF)
- Sponsor decision (specify reason in the eCRF)
- Noncompliance with study protocol
- Other (specify reason in the eCRF)

7.12.1.2 **Discontinuation from Study**

A participant may be discontinued prematurely from the study (in its entirety) for the following reasons:

- AE (including hospitalization for COVID-19/sequalae)
- Withdrawal by participant (specify reason in the eCRF)
- Lost to Follow-up
- Death
- Physician decision (ie, Investigator decision specify reason in the eCRF)
- Sponsor decision (specify reason in the eCRF)
- Noncompliance with study protocol
- Other (specify reason in the eCRF)

If a participant is withdrawn because of an adverse experience, the participant will be followed and treated by their health care provider (with documented follow-up) until the abnormal parameter or symptom has resolved or stabilized.

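### The protocol does not settle what happens after a positive test beyond 48 hours, so the hospital and emergency-visit endpoint can lose events it is meant to count

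*Combined protocol and SAP*

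**What the plan says.** One case has a clear rule. Under 6.6.1, for participants positive within 48 hours of baseline, "they will be considered unevaluable for the study endpoint and will be discontinued".

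For later positives, which are the ones that count as primary events, the passages point in two directions.

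*Toward leaving the study*
- 3.3: "Participants that test positive for COVID-19 will be encouraged to complete early termination assessments and record their symptoms using the COVID-19 symptom list".
- 3.3.1 treats the early termination questionnaire, completed after the last treatment, as one way of completing the study.
- 6.6.5: "Participants that discontinue the study early due to COVID-19 infection or are hospitalized for any reason are encouraged to attend the early termination assessment". Leaving because of infection is named as something that happens, but no passage says when.

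*Toward staying, possibly on spray*
- 5.3 instructs participants to dose "with the nasal spray for 28 consecutive days" and makes no exception for infection.
- 7.12.1 asks investigators to "encourage participants who prematurely discontinue treatment to remain in the study as appropriate".
- 7.12.1.1 and 7.12.1.2 list "AE (including hospitalization for COVID-19/sequalae)" among the reasons for which a participant may stop drug or study. A positive test alone is not listed.
- 3.1 sets a secondary aim to "assess the safety and tolerability of use of NONS in participants with COVID-19". The Synopsis and 2.2 have related tolerability objectives.

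On analysis, 9.5.2 dates the secondary event at the hospital or emergency visit whether the positive result came earlier or later, and runs the analysis in the same way as the primary. The primary analysis (9.5.1) censors anyone who stops the spray for any reason.

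**The concern.** The secondary endpoint is largely an event of people who are already infected. Under 9.5.2 a hospitalised participant who tests negative does not count, and a visit after a positive test does. The participants at risk of a secondary event are therefore mainly those whose handling the protocol leaves open.

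If participation ends at the positive test, or follow-up time is censored because the spray was stopped, these people leave the risk set just before the event can occur. If some instead keep spraying, the secondary effect also includes whatever the spray does after infection. Section 1.5.1 gives a reason to think that could matter: in the sponsor's trial in mild COVID-19, mean viral RNA was lower on NONS than on placebo by a factor of 16 at Days 2 and 4. What the secondary hazard ratio measures thus depends on a choice that the protocol does not state.

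**Working it through.** **One case under each reading.** Take a participant who tests positive on Day 13, is not admitted, and visits an emergency department on Day 20.

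1. *Terminated at the test (3.3, 3.3.1, 6.6.5).* The early termination questionnaire is completed near Day 13 and counts as study completion. Under 7.12.1.3, procedures are completed at or near discontinuation. The Day 20 visit falls after efficacy reporting has ended.
2. *Stops the spray but stays (7.12.1).* The visit can be reported at the Table 4 contacts. If the 9.5.1 rule is carried over, the participant is censored at the last status submission, which 9.5.1 explains as the last day confirming no positive test. Read that way, censoring falls before Day 13 and the visit is lost. If that explanation is ignored and the diary continues, the visit could count. The text allows both.
3. *Continues the spray (5.3).* The visit counts, and the effect includes dosing after infection.

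The same visit is counted or lost depending on the reading.

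**The plan's primary figures (inputs from 9.2).** Hazard ratio 0.15, two-sided 0.05, 90% power, 5,740 per arm, placebo rate 0.000075 per day, 25% censored by Day 28.

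- Schoenfeld events: (1.960 + 1.282)² / (0.25 × (ln 0.15)²) = 11.68, rounded up to 12. Power with 12 events is 90.8%.
- Censoring hazard c = −ln(0.75)/28 = 0.01027 per day.
- Expected cases per arm: n × λ/(λ + c) × (1 − exp(−28(λ + c))). Placebo (λ = 0.000075) gives 10.5. NONS (λ = 0.15 × 0.000075) gives 1.6. The total is 12.0.

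This agrees with the plan's 10 and 2. Because 9.5.1 places the primary event at specimen collection, later dosing or follow-up changes none of these figures.

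**Number of people and amount of follow-up.** There are about 12 cases at design and 18 at the closing threshold in 9.2. With the same hazards, the mean time of infection is Day 13.3, leaving 28 − 13.3 = 14.7 days of scheduled dosing and secondary follow-up.

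The share of cases whose visit would fall by Day 28, if it came L days after the test, is (1 − exp(−(28 − L)(λ + c))) / (1 − exp(−28(λ + c))). The lag is an assumption:

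| Lag L | Visit by Day 28, full follow-up | Visit observed if follow-up ends at the test |
|---|---|---|
| 3 days | 91% | 0% |
| 7 days | 78% | 0% |
| 14 days | 54% | 0% |

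The middle column assumes no other loss between test and visit.

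**Expected secondary events.** The documents give no visit rate among cases. Assuming 1% to 20%:
- 12 cases: 12 × 0.01 = 0.12 to 12 × 0.20 = 2.4.
- 18 cases: 18 × 0.01 = 0.18 to 18 × 0.20 = 3.6.

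At a hazard ratio of 0.15 and design case numbers, visit rates of 5%, 10% and 20% give nominal power of about 11%, 18% and 31%. The Schoenfeld approximation is rough at such counts. As a cross-check, if every event fell on placebo, an exact 1:1 split test would need six events for two-sided significance: 2 × 0.5⁶ = 0.031, against 0.0625 with five.

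**The case against.** Much of the case on the other side stands.

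- Section 3.3 encourages an assessment. It does not mention the spray and does not order anyone out. A reader might infer that every positive participant is removed; the text does not say so.
- The lists in 7.12.1.1 and 7.12.1.2 are permissive and open-ended, and 7.8 makes a COVID-19 diagnosis an adverse event of special interest. They are not a rule that only hospitalised participants stop. The sentence in 6.6.2, "Participants that are hospitalized for COVID-19 only are considered treatment failures", is a classification and is silent on dosing.
- The tolerability objective does not require spraying after infection. Section 2.2 covers all participants, and tolerability can be judged from earlier doses.
- Section 6.5 says the instructional materials cover what to do on a diagnosis. Those materials are not in these documents, so it cannot be shown that sites lack a rule or will act differently.
- Treatment is blinded, so varied handling is not tied to arm and does not by itself bias the randomised comparison.
- Much of the machinery exists: separate sections for stopping drug and leaving the study, dose dates in the diary, Table 4 reporting of hospital and emergency visits to Day 35, and follow-up of events of special interest (7.9).

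The last point lowers the cost of a fix but does not close the gap. No passage applies these provisions to a positive participant, and data gathered for safety do not enter the secondary analysis if the participant has already been censored. Blinding does not bring back lost events.

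**Conclusion.** The point holds as a gap with conflicting implications. Beyond 48 hours, neither study participation nor dosing after a positive test is settled, and two of the available readings can remove participants before the secondary event that 9.5.2 says should count.

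Its reach is limited to the secondary endpoint. Expected secondary events are about 0.1 to 3.6 on the assumed 1% to 20% visit rate and 12 to 18 cases, so that endpoint is nearly uninformative either way. With so few events, however, the handling of one or two participants could change the result.

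Three stronger conclusions are not supported:
- *The endpoint will mix prevention with treatment of infection.* That follows only if some participants continue spraying.
- *The secondary result cannot support its objective.* The objective in the Synopsis, 2.2 and 9.5.2 is fewer medical interventions or less severe disease, and both fewer and milder infections serve it.
- *The difference in who stops the spray can be given a figure.* The documents supply neither a stopping rule nor a hospitalisation rate from which to calculate one.

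The verdict rests on reading 9.5.2 as carrying over the 9.5.1 censoring rule, and on there being no overriding rule in the materials not supplied.

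**What to change.** 1. Amend 3.3, 3.3.1 and 6.6.5 so that a positive test after 48 hours does not by itself end study participation. Collect hospital and emergency visits through Day 28 whether or not the spray is continued. The Table 4 contacts to Day 35 already provide for this.
2. In 9.5.2, give the secondary endpoint its own censoring rule: no censoring at a positive test or at stopping the spray. State that the effect covers whatever dosing follows infection.
3. Reconcile the tolerability objectives in the Synopsis, 2.2 and 3.1 with 3.3, 5.3, 6.6.1, 6.6.5 and 7.12.1 in one statement on study treatment after a positive test, and align the participant instructions with it. The choice of rule is the sponsor's clinical decision.

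The cost is protocol wording, site and participant instructions, and continued contact with about 12 to 18 participants. Sample size and the primary analysis do not change.
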